1.2.4 Models of Programs that Include Sharing Genetic Results with Patients

The Massachusetts General Hospital Cancer Center (MGHCC) has recently begun promoting their efforts to share genetic results with treating physicians for rapid application into the clinic. MGHCC was the group that first reported that NSCLC patients positive for ALK rearrangements responded to the ALK inhibitor crizotinib, leading the multi-institutional collaboration that tested the drug in the expanded cohort.[7] Their Translational Research Lab (TRL) currently screens patient tumors for 120-130 specific mutations in ~15 genes. Precise robotic technology allows the TRL to process up to 100 specimens in a day, allowing for rapid genetic profiling and communication of results within a month of testing.[14] Post-testing, the treating physician informs the patient about any genetic variants identified that can be treated with targeted therapy, or that may render them eligible for enrollment into a clinical trial evaluating therapy targeted against their variant. Samples are stored so they can be re-tested if new variants (and trials designed to evaluate drugs to treat them) are discovered in the future.[14] While this system has been informative, the MGH approach employs an outdated sequencing approach based on primer extension technology. The UNC effort will identify a much larger class of variants (e.g., deletions, amplifications) in a much larger number of genes (>200) using Next Generation sequencing techniques.

Another interesting model for rapid genetic profiling specifically geared towards clinical application can be found at the Clarity Foundation (www.clarityfoundation.org). The mission of this foundation is to improve treatment outcomes in recurrent and progressive ovarian cancer by providing molecular analysis of tumor specimens upon request from physicians. Through partnership with CLIA-certified labs, the foundation offers access to molecular tests provided formalin-fixed paraffin-embedded (FFPE) tumor blocks, unstained slides, or fresh frozen tissue specimens are available. The panel of tests they run includes biomarkers targeted by commercially available and investigational drugs, as well as biomarkers indicating sensitivity or resistance to certain chemotherapy. Test results are provided as soon as 7 days after receipt of the sample, with full reports provided in 4 weeks. They have been providing this service for almost three years. The Foundation also offers profiling of newly diagnosed patients not for immediate application, but in the event the patient recurs in the future.

Patients have brought results of their genetic tests from outside laboratories to UNC clinicians, including tests conducted in the Clarity Foundation partner labs, but concerns exist surrounding the application of these results to guide clinical care. While the Scientific Advisory Board of this foundation includes high-level representatives from respected institutions in the field of oncology (e.g. Memorial Sloan Kettering, Dana Farber Cancer Institute, etc.), relying on this type of testing with uncertain validation could be problematic. From a review of the tests offered

via Clarity Foundation's website, the investigators at UNC-CH would not consider many of these tests to be of accepted clinical utility.

While very little data exist regarding communication of individual genetic results to cancer patients participating in trials, results to date are encouraging. A recent pilot study evaluated the impact of sharing results of the germline *CDKN2A* mutation in a subset of melanoma survivors who had participated in a Genetics, Environment and Melanoma (GEM) study at the University of Michigan hospital. This mutation confers a risk of 30-65% through age 80 for development of melanoma, and a 5% risk for another melanoma among melanoma survivors.[15]

The majority (70%) of people enrolled in the pilot trial (n=19 of 27 contacted) opted to be told whether they carried a *CDKN2A* mutation, and investigators reported the knowledge did not cause the participants emotional distress (measured 1 week and 3 months after disclosure) or change their health behavior.[15] Of note, subjects received educational materials about risk factors for melanoma and reviewed these materials with a genetic counselor prior to disclosure of their mutational status by the genetic counselor.[7] In addition, most participants indicated an increased willingness to participate in genetic research in the future because of disclosure. Of note, LCCC1108 focuses on communication of genetic results from somatic profiling of tumor tissue, and does not focus on germline genetic profiling. Germline changes discovered and deemed clinically relevant, however, will be reported to patients in the context of formal genetic counseling.

1.3 Using Genotyping to Treat: a Prospective Pilot Study

Treating patients based on genetic variants, a so-called "genome-forward approach", has been applied across tumor types, with clinical benefit reported in a prospective pilot study. Von Hoff and colleagues published a multicenter, single arm pilot study of patients with a wide variety of refractory cancers that utilized molecular profiling to select "targeted" treatment.[16] Molecular targets were detected via oligonucleotide microarray (MA) gene expression assays on fresh (frozen) biopsy tissue, and via immunohistochemistry (IHC) and fluorescent in situ hybridization (FISH) on formalin-fixed tissue. A list of possible therapies based on targets was generated based on an extensive review of the literature and using data from a prior retrospective feasibility study. These agents included those that are traditionally considered targeted against a particular molecule (e.g., trastuzumab for HER2/Neu) as well as those not traditionally considered targeted drugs (e.g., irinotecan for carboxylesterase (CES-2)). In this pilot study of 86 patients, 66 were treated according to molecular results.[16]

In terms of efficacy, patients served as their own control; progression-free survival (PFS) post "molecularly-targeted" treatment (PFS-MT) was compared within individual patients to PFS after their most recent regimen (PFS-RT). Of the 66 patients treated according to molecular results, 27% had a PFS ratio of ≥ 1.3 (PFS-MT/PFS-RT).

Researchers also documented the choice of therapy the treating physician would have chosen without molecular results available, and none of them matched the targeted therapy.[16]

1.4 LCCC1108: Study Overview

Patients with a diagnosis or potential diagnosis of cancer will be consented for enrollment into this study. In clinics in which the IRB-approved Cancer Survivorship Cohort (CSC, LCCC0906) is operating, eligible patients for LCCC1108 may be offered enrollment into the CSC via the CSC global consent if they are eligible for LCCC0906. In clinics in which the CSC is or is not yet operational and/or the patient is not eligible (or has declined LCCC0906 participation), LCCC1108 will function as a stand-alone protocol. Patients deemed eligible for LCCC 1108 who may have been offered the opportunity to enroll into CSC prior to LCCC1108 initiation) and who have stored tumor tissue samples in the Tissue Procurement Facility (TPF) may be contacted via telephone for enrollment into LCCC1108 and to obtain consent for research access to their stored tumor tissue.

Specimens collected under LCCC1108 consent will be stored in the TPF along with any specimens previously collected as part of routine clinical care and stored under the general TPF banking protocol (LCCC9001), under the CSC global consent, under this protocol, or under another approved tissue banking protocol for consented participants. Genomic DNA or RNA will be obtained either as part of the CSC (and handled and stored by the Biospecimens Core), or under LCCC1108. Appropriate tissue and possibly germline DNA and RNA will be released for molecular analysis to UNC's High Throughput Sequencing Facility or other UNC research facility. Medical records will be abstracted to facilitate correlation of clinical data with genetic testing in studies using the mechanisms approved for the CSC.

It is expected that most LCCC1108 participants will provide samples through procedures that are part of their standard clinical care, and thus, the additional risk of providing tissue to be used in this research will be minimal. Many participants will already have tissue and/or blood specimens banked in TPF under the general TPF protocol (LCCC9001) or under another approved tissue banking protocol. Others, who are consented to LCCC1108 pre-operatively, will allow any surplus tissue and/or blood (after the standard diagnostic procedures have been completed) to be accessed, stored, and processed for the research described herein. Parental consent is required for all patients <18 years old. Separate consent documents are also required for minor children (7-14 years old) and adolescents (15-17 years old). Any participant <18 years of age must have tissue already banked, or be undergoing a procedure as part of their standard clinical care.

A subset of patients ≥ 18 years of age will be asked to submit tissue and blood specimens obtained from procedures without a specific identified clinical or diagnostic need, based on current clinical standards of care. Biopsies of vital organs (e.g., lung, liver etc.) will be restricted to those participants ≥ 18 years of age whose treatment offers no expectation of cure, such as patients with refractory solid tumors who relapse with metastatic disease, e.g. Other biopsies performed outside of clinical standard of care will be limited to those tumors that can be accessed without subjecting the participant to unreasonable risk, as determined by the physician performing the procedure.

Specimens will be analyzed for alterations in a panel of specific genes of cancer relevance, but only genetic variants of potential clinical interest will be released to the treating physician to disclose to the patient. Germline changes that are discovered by systematic analysis and deemed clinically relevant will be reported in the context of formal genetic counseling. Results of genetic tests from the “gene list” will be analytically validated in a CLIA-certified laboratory prior to distribution to the treating physician (see possible exception to this requirement noted below). Note: when results between NextGen sequencing and CLIA are discordant, results from the CLIA-certified laboratory only will be distributed to the treating physician.

LCCC1108 Molecular Tumor Board (MTB) reviews the sequencing information and identifies the genes of relevance based on CCGR recommendations to move forward for clinical confirmation. This tumor board provides additional oversight, ensuring compliance with the protocol, technical quality assurance, and appropriate application of results to individual patients. This board is comprised of representatives of the CCGR, the Pathology committee, key laboratory scientists involved in technical and bioinformatic aspects of UNCseq™, and clinical/molecular pathologists.

The sequencing data and outcomes from the CLIA confirmation assays are reviewed in aggregate to ensure quality assurance measures are being met. Our confirmation rate historically is greater than 95%.

1.4.1 UNC Clinical Committee for Genomic Research (CCRG)

The UNC CCGR has been established per the NHLBI recommendations cited earlier.[10] This group will meet quarterly to review and update the list of reportable tests, and in what setting each test would be clinically relevant based on its potential for clinical application. See Appendix A for the CCGR Charter. In brief, the Committee will categorize reportable tests into 3 lists:

- **List #1:** Genetic alterations of accepted clinical utility (and validated (whether confirmed or refuted) in a CLIA certified laboratory) used in standard of care (SOC) management of patients (e.g., KRAS in mCRC)

- **List #2:** Genetic alterations of potential clinical significance (and validated (whether confirmed or refuted) in a CLIA certified laboratory for use in non-SOC settings (e.g., EGFR in breast cancer)
- **List #3:** Genetic alterations of potential clinical significance (without the possibility of validation in a CLIA certified laboratory for use in non-SOC settings (e.g., LKB1)

As of the writing of Amendment #6, a List #4 is under consideration by the CCGR. This list would include genetic variants that predict sensitivity to non-targeted treatment (e.g. radiation, cytotoxics).

In developing the lists, the Committee will receive input from the LCCC Oncology Disease Groups (e.g., Breast Cancer, Lung Cancer) and the LCCC1108 Pathology Committee (see Appendix A). For List #3, when validation in a CLIA certified laboratory is not available or possible, results of NextGen sequencing will be provided to the patient through the treating physician on a “compassionate use” basis, but only if the following criteria are met (which we anticipate will be rare):

- The UNC Committee deems the information would be of clinical interest
- The patient has advanced cancer for which there is no standard of care
- Results are reproduced in the research laboratory using NextGen sequencing
- The results include a statement that “This is a research result from a non-validated test environment”
- A waiver for the CLIA-certification requirement is obtained from the UNC IRB on a case-by-case basis.

Similar to the program established at MGHCC, we will not share tests performed at UNC with treating physicians unless they can potentially inform the care of a particular patient disease population.

1.4.2 Treatment Decisions

Ideally, reportable findings in patients with refractory disease (after confirmation by validation in a CLIA certified laboratory) will be used to influence the choice of a clinical trial when standard of care options are exhausted (e.g., identification of a PI3K mutation may lead the treating physician to choose a trial that includes a PI3K inhibitor if the patient meets eligibility criteria). Clinical trials may not be available in all such patients, however. Therefore, in patients for whom there is no available trial, the finding of an unexpected, but targetable variant could lead to the off-label use of an approved therapy. For example, a small percentage of patients with ovarian cancer will be found to harbor activating KIT mutations, and such patients could be treated with anti-KIT agents (e.g. dasatinib) based on results of NextGen analysis (with re-testing in a CLIA certified laboratory) even though dasatinib is not presently approved for use in ovarian cancer.

Use of results of the UNCseq™ intervention from the “Gene List” as the basis for treatment or to refer a patient to a clinical trial, will be up to the discretion of the treating physician,. Treatment decisions will be documented via use of the UNCseq™ Physician survey (an IRB-approved survey provided separate from this protocol) and review of medical records. If treatment is based on molecular testing, the specific treatment (including referral to a clinical trial, or choice of commercial agent(s), dose and duration) will be documented when this information is available.

It is expected that any therapy chosen based on this list by the treating physician will be carried out using the most current prescribing information for that therapy available from the FDA, and/or based on a review of the scientific literature for that particular tumor type. Outside of a clinical trial, we anticipate that most physicians will evaluate tumor response every 6-8 weeks (or other as per standard of care for the particular tumor type) as they would when starting any patient on a new anti-cancer therapy. These data will be recorded, as will the date of progression (if available) and patient survival.

1.4.3 Characterization of Population and Treatment Outcomes

While several attempts have been made to document the proportion of specific genetic alterations in selected Phase I populations, the intervention in LCCC1108 will provide the opportunity to characterize the proportion of most of the known clinically relevant genetic alterations across a wide variety of tumors. [17-19] Specifically, as a primary objective, we will estimate the proportion of enrolled patients who have undergone successful sequencing and who have a reportable genetic variant identified via UNCseq™. The study intervention, includes the use of highly and ever evolving sequencing methods and genomic technologies that may be applied to both somatic and germline tissues, and correlated with extensive clinical annotation and outcome data. These technologies may associate known molecular alterations in a variety of tumors with prognosis and/or clinical outcomes. A primary objective of this study is to compare PFS ratios between cancer patients with active disease with a reportable genetic variant and those without a reportable genetic variant. We chose the PFS ratio as it is the approach already used and published by Von Hoff, and it allows the patient to serve as his or her own control. Whether disease is defined as active or not takes place at the time of the MTB meeting. In this context, a patient is considered to have active disease provided they have not been declared to have NED (no evidence of disease) and they are not in hospice. The PFS ratio is defined as the PFS after the first treatment post UNCseq™ results divided by the PFS post the most recent therapy prior to UNCseq™ on which the patient has just experienced progression. See section 4.4 for additional details on this endpoint.

Using clinical data from patients enrolled in this protocol, either through LCCC0906 (the CSC) or LCCC1108, we plan to facilitate explorations of any correlation between these genetic alterations and response to molecularly based treatment under this and future IRB-approved protocols. As a secondary

objective, we will compare PFS ratios between patients with active disease and a reportable genetic variant who were treated based on this variant versus those not treated based on this variant (see section 4.4).

1.5 Rationale

By sequencing targeted regions of a subject's tumor genome, and returning relevant and individual results to the treating physician, we hope to provide a mechanism for rapid, patient-specific treatment decisions. These data will become part of the patient's information in the CSC database if they have consented to be part of that study.

The number and type of situations appropriate for patient-specific approaches to cancer treatment are expected to grow as scientists, including those at UNC, discover new molecular alterations across a broader range of tumor types. These discoveries are essential, as traditional approaches to treatment have made limited progress over the past several decades, and virtually none against advanced solid tumors.[20]

Patient samples and/or data from this repository may also be submitted to the National Institutes of Health (NIH), National Cancer Institute (NCI) repository for the purposes of Genome-Wide Association Studies (GWAS).

2.0 STUDY OBJECTIVES

2.1 Primary Objectives

- 2.1.1 To estimate the proportion of patients enrolled in LCCC1108 who have undergone successful sequencing (see section 6.0) and have a reportable genetic variant identified via UNCseq™
- 2.1.2 To estimate 2 year PFS in cancer patients with active disease (defined in section 1.4.3) with a reportable genetic variant and those without a reportable genetic variant

2.2 Exploratory Objectives

- 2.2.1 To estimate differences in PFS between cancer patients with active disease with a reportable genetic variant who were treated based on variant, versus those who were not treated based on a variant.
- 2.2.2 To collect and describe clinical data (e.g., medical history, demographics) including treatment outcomes after availability of UNCseq™ results in patients
- 2.2.3 To link tumor samples and other biospecimens for future IRB approved clinical trials that have a tissue specimen component

2.3 Primary Endpoints

- 2.3.1** The proportion of those patients with successful sequencing (see section 6.2) who have any non-standard of care variant discovered via UNCseq™ and confirmed after UNCseq™ in a CLIA certified laboratory (or provided by a waiver by the IRB).
- 2.3.2** PFS is defined as the time from day 1 of treatment until disease progression or death as a result of any cause.

2.4 Exploratory Endpoints

Other efficacy outcomes that may be evaluated include objective response (OR), stable disease (SD) and overall survival (OS), and will be defined as per RECIST1.1 or per the appropriate hematologic disease guidelines [21-26]. Treatment decisions using UNCseq™ are based on the treating physician's responses to the UNCseq™ Physician survey (an IRB-approved survey provided separate from this protocol).

3.0 PATIENT ELIGIBILITY

3.1 Inclusion Criteria

Patients must fulfill all criteria to be eligible for this study:

- 3.1.1** Current or prospective cancer patients; current cancer patients must have histologically or cytologically confirmed diagnosis of cancer
- 3.1.2** Patients who are considering enrollment in LCCC1108, who are eligible for the CSC, and who are seen in a clinic at UNC in which the UNC Health Registry/CSC is operational may be offered enrollment into the CSC via the CSC global consent; however participation in the CSC is optional and patients can enroll in LCCC1108 alone. Patients deemed eligible for LCCC 1108 who have enrolled into CSC or another study that included banking of tumor tissue prior to LCCC1108 initiation (and who have tumor tissue already stored) may be contacted via telephone for enrollment into LCCC1108 for access to their stored tumor tissue. Telephone consenting will be documented properly per IRB guidelines.
- 3.1.3** Participant must have tumor tissue available and suitable for molecular analysis from at least one of the following sources:
- Tissue previously stored at UNC, Chapel Hill, NC (e.g., tissue collected under the CSC (IRB # 09-0605), IRB # 01-1283, IRB #90-0573, IRB#09-0768, or IRB #05-2015)

- Tissue previously stored at an outside institution (other than UNC-CH), provided investigators can determine that the tumors were sampled and stored under appropriate conditions for inclusion in LCCC 1108 study
- Patient is undergoing tissue collection as per clinical standard of care and is willing to allow specimens from surplus tissue to be diverted for research purposes
- Patient is undergoing tissue collection as per clinical standard of care and is willing to have additional specimens taken for research purposes
- Patient is willing to undergo biopsy to procure tissue samples for research purposes only without a previously identified clinical or diagnostic need

3.1.4 For those ≥ 18 years old capable of providing informed consent and willing to sign the IRB-approved written informed consent agreements for the present protocol

3.1.5 For minor children 7-14 years of age, and adolescents 15 to 17 years of age, capable and willing to provide informed consent; parental consent also required.

The following additional inclusion criteria apply only to patients undergoing biopsy for research purposes only under this protocol (i.e., without a previously identified clinical or diagnostic need):

3.1.6 ≥ 18 years of age

3.1.7 Treatment options offer no expectation of cure (e.g., advanced solid tumor patients with metastatic disease) **NOTE:** This restriction applies to biopsy of vital organs only (e.g., lung, liver)

3.1.8 Appropriate candidate for research biopsy based on institutional standards for target biopsy site

3.2 Exclusion Criteria

Patients who fulfill any of the following criteria will be excluded:

3.2.1 Any condition that would make participation in the protocol unreasonably hazardous for the patient in the opinion of the treating physician

[figure not shown]
3.2.2 Affected by dementia, altered mental status, or any psychiatric or co-morbid condition that would prohibit the understanding or rendering of informed consent

The following additional exclusion criteria apply only to enrolled patients undergoing biopsy for research purposes only:

3.2.3 History of serious or life-threatening allergic reaction to local anesthetics (i.e. lidocaine, xylocaine) or any medications used for conscious sedation (if applicable)

- 3.2.4 Requires general anesthesia for collection of biopsy
- 3.2.5 Currently pregnant or lactating
- 3.2.6 Active cardiac disease, defined as:
 - a. History of uncontrolled or symptomatic angina.
 - b. History of uncontrolled arrhythmias
 - c. Myocardial infarction < 3 months from study entry
 - d. Uncontrolled or symptomatic congestive heart failure
 - e. Any other cardiac condition, which in the opinion of the treating physician would make this protocol unreasonably hazardous for the patient
- 3.2.7 Patients receiving bevacizumab less than 6 weeks prior to enrollment into this study should not undergo research core biopsies because of the concern for potential increased bleeding risk and delayed healing. (**NOTE:** Patients receiving bevacizumab who are undergoing a research biopsy of accessible organs (e.g. breast, lymph node, skin etc.) must be two weeks from the last dose of the angiogenesis inhibitor).

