4.1.3.1 Blood Samples

During screening, potential study subjects should be queried about any medications they are taking (see Eligibility Criteria). If applicable, a pregnancy test (blood or urine) should be done. For patients undergoing biopsy, the physician performing the procedure will ensure the patient meets all institutional standards for the procedure, and may collect ~8mLs in a single yellow top ACD tube (i.e., collection of normal tissue is not required). Alternatively, the participant can have a blood sample obtained during pre-operative care or in the outpatient phlebotomy clinic as appropriate. Inpatient participants may have blood samples taken as part of their regular phlebotomy draw.

For eligible patients who are not undergoing biopsy, a single yellow top ACD tube may be collected (~8 mLs of blood) for storage within 28 days of consent (if

possible), unless the investigator deems another source of normal DNA (or RNA) is more appropriate (see below).

For storage, serum will be processed by and stored in TPF, with each aliquot assigned a unique identification code, as per standard TPF procedures. Genomic DNA (or RNA) may be obtained and appropriate germline DNA (or RNA) may be released to the High Throughput Sequencing Facility or other UNC research facility for molecular analysis.

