4.1.4 Tumor Biopsy Collection

Research Biopsies

In order to minimize the risk of a tissue procurement procedure (biopsy, thoracentesis, or paracentesis, e.g.), only qualified personnel will perform these procedures. Prior to the procedure, the physician performing the procedure will ensure the patient meets institutional standards for the procedure, discuss the risks with each study participant, answer any questions, and obtain separate procedure consent.

For biopsies of lesions that are not superficial and clearly palpable, imaging studies such as CT or ultrasound will be used to guide the biopsy in order to minimize the risk of damage to adjacent structures. Under sedation, biopsies will be made with an 11g -18g core needle depending on site and judgment of the physician performing the biopsy, with a maximum of 4-6 passes through tumor made if this is felt to be safe by the physician performing the biopsy procedure. Alternatively, surgical excision of superficial sites of disease is also appropriate if

preferable to the patient over needle biopsy. After lymph node biopsies, patients will be observed for approximately 2 hours (range 2-4 hours) after the procedure, or per institutional standard guidelines. After liver biopsies, patients will be observed for approximately 4 hours (range 4-6 hours) after the procedure, or per institutional standard guidelines.

Biopsies will be immediately snap-frozen by research personnel using standard procedures, stored in the TPF facility in a -70°C freezer, and given a unique identification code. Genomic DNA or RNA will be obtained and appropriate tissue DNA or RNA released to the High Throughput Sequencing Facility or other UNC research facility for molecular analysis.

Biopsy/Surgery as Part of Routine Clinical Care

Tumor biopsy samples and surgical specimens will also be eligible for genotyping in patients scheduled to undergo biopsy and/or surgery as part of routine clinical care. In this situation, patients will be consented to have additional specimens taken for research purposes only, and/or to have any excess tissue remaining after clinical purposes are satisfied analyzed for molecular alterations (via LCCC0906, if possible). Researchers will ensure that the tumors were appropriately sampled and stored for inclusion in this study. If a blood, buccal sample, or other normal specimen is not collected during the procedure, patients may be asked to provide one as soon as practicable (see 4.1.3).

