4.3 Expected Risks

Pain or discomfort related to the procedure is minimized with the use of sedation. Patients who require general anesthesia to undergo a separate biopsy procedure for research purposes only are not eligible for LCCC1108.

Biopsy Risks

Potential adverse effects of biopsy include bleeding (which can necessitate a blood transfusion and/or hospitalization, and can be life-threatening) and infection, both with very low frequencies. Bleeding at the time of biopsy will be controlled by standard clinical procedures. Damage to local structures will be minimized by knowledge of local anatomy and standard pre-biopsy imaging studies. Other risks related to biopsies are dependent on the site of the biopsy. These are described in the LCCC1108 informed consent.

Local Anesthesia

With regard to anesthesia, all biopsy procedures require local anesthesia using lidocaine, xylocaine, or related compounds. There is a small risk of an allergic reaction associated with these drugs. In order to minimize the risk of local anesthesia, only qualified personnel will perform the biopsy procedure. Patients will be queried if they have had previous allergic reactions to local anesthetics.

Intravenous Conscious Sedation

Certain biopsy procedures, such as lymph node or liver biopsies, may require intravenous conscious sedation (IVCS). IVCS is a minimally depressed level of consciousness that retains the patient's ability to maintain continuously a patent airway independently and respond appropriately to physical stimulation and verbal commands.

The medications used to induce conscious sedation include the benzodiazepine midazolam and the opioid agonist fentanyl, or as per standard of care. IVCS is performed once over a 30-60 minute period, and may require administration of multiple doses of each agent over this time frame. Rarely, IVCS will last longer than 60 minutes.

Midazolam:

See <http://www.drugs.com/pro/midazolam-injection.html> for complete prescribing information on midazolam, including complete information on risks associated with its use.

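### The 6-week bevacizumab window for research core biopsies is counted to enrollment instead of to the biopsy, so a dose given after enrollment escapes it at non-accessible sites

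*Combined protocol and SAP*

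**What the plan says.** Criterion 3.2.7 in section 3.2 (Exclusion Criteria) reads "Patients receiving bevacizumab less than 6 weeks prior to enrollment into this study should not undergo research core biopsies", and the reason follows at once: "because of the concern for potential increased bleeding risk and delayed healing". A NOTE in the same criterion treats accessible organs (breast, lymph node, skin and the like) separately. Patients on bevacizumab who have those sites biopsied "must be two weeks from the last dose of the angiogenesis inhibitor"; enrollment is not mentioned.

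The criterion belongs to a group introduced by "The following additional exclusion criteria apply only to enrolled patients undergoing biopsy for research purposes only". It therefore concerns a procedure that may follow enrollment and has no identified clinical need.

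Other sections that bear on the point:

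- Section 4.1.3.1 (Blood Samples): "During screening, potential study subjects should be queried about any medications they are taking". No repeat query before the biopsy is stated.
- Section 3.1.8: "Appropriate candidate for research biopsy based on institutional standards for target biopsy site".
- Section 4.1.4 (Tumor Biopsy Collection): "Prior to the procedure, the physician performing the procedure will ensure the patient meets institutional standards for the procedure".
- Sections 1.4 and 3.2.1: general physician judgment about unreasonable risk or hazard.

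**The concern.** Bleeding and poor healing are hazards of the needle procedure. The relevant interval runs from the last dose to the biopsy, and enrollment is only an administrative date between the two. A window that ends at enrollment says nothing about a dose given afterwards.

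The consequence is a participant-safety gap in a research-only procedure. Section 4.1.4 provides for 11g to 18g core needles with a maximum of 4 to 6 passes, and it refers to liver biopsies. Section 4.3 describes biopsy bleeding as something "which can necessitate a blood transfusion and/or hospitalization, and can be life-threatening", while putting its frequency as very low. Where a dose follows enrollment, the 6-week limit does not operate for non-accessible sites, and protection falls back on the proceduralist's general check.

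**Working it through.** The plan gives no figure to reproduce here. The check is date arithmetic on the literal rule, followed by a search for any other section that supplies the missing interval.

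**Inputs from the protocol.** The 6-week window ending at enrollment, and the two-week rule from last dose for accessible sites (both in 3.2.7). The documents do not give the time from enrollment to biopsy or the frequency of bevacizumab dosing in that period, so all dates below are assumptions.

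**Notation, in weeks.** *d* = last pre-enrollment dose to enrollment; *g* = enrollment to biopsy; *r* = enrollment to a later dose, with *r* < *g*. For non-accessible sites, 3.2.7 tests only whether *d* ≥ 6.

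**1. No dose after enrollment.** Dose-to-biopsy interval = *d* + *g*. Since *g* ≥ 0, *d* ≥ 6 guarantees at least 6 weeks. Example: *d* = 7 and *g* = 3 give 10 weeks. The rule protects.

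**2. A dose after enrollment.** Dose-to-biopsy interval = *g* − *r*. The tested quantity *d* has dropped out, so passing the criterion places no lower limit on the interval. Example: *d* = 7 weeks, *r* = 2 weeks = 14 days, liver core biopsy 3 days after that dose, so *g* = 14 + 3 = 17 days. Interval = 17 − 14 = 3 days, against an intended 6 × 7 = 42. The criterion is met because 7 is not less than 6. A patient who first starts bevacizumab after enrollment has no pre-enrollment dose for the rule to test, so the 6-week wording does not reach that patient at all.

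**3. Final dose shortly before enrollment, late biopsy.** The patient is barred when *d* < 6, even if *d* + *g* ≥ 6, that is *g* ≥ 6 − *d*. Example: *d* = 3 and *g* = 5 give 8 weeks, yet the biopsy is refused. This error is conservative.

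| Case | Interval tested by 3.2.7 (non-accessible site) | Dose-to-biopsy interval | Literal rule | If counted to biopsy |
|---|---|---|---|---|
| *d* = 7, *g* = 3, no later dose | 7 weeks | 10 weeks | not barred | not barred |
| *d* = 7, dose at 2 weeks, biopsy 3 days later | 7 weeks | 3 days | not barred | barred |
| *d* = 3, *g* = 5, no later dose | 3 weeks | 8 weeks | barred | not barred |

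**4. Comparison with the NOTE.** Take the second row and make the site a lymph node. Three days is short of two weeks from the last dose, so the NOTE bars the biopsy. For liver, 3.2.7 does not. The sites given the longer washout lose it in this case, while the sites given the shorter one keep it.

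**5. Other sections.** The medication query in 4.1.3.1 is placed at screening. Sections 1.4, 3.1.8, 3.2.1, 4.1.3.1 and 4.1.4 contain physician or institutional-standard checks, none with a bevacizumab interval. No section limits the time from enrollment to biopsy or bars bevacizumab in between.

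**The case against.** The strongest reply is that the failing case needs several things at once: a research-only biopsy, a non-accessible site, bevacizumab started or restarted between enrollment and biopsy, and a proceduralist who goes ahead regardless. A patient already dosed within 6 weeks before enrollment is barred whatever happens later.

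Section 4.1.4 also makes the number of passes conditional on the performing physician's view of safety, and requires a discussion of risks and a separate procedure consent. The institutional standards it relies on are not in the documents and may contain a bevacizumab interval of their own. The purpose of 3.2.7 is plain from its stated reason, and counting to entry follows a convention used nearby: 3.2.6 counts recent myocardial infarction to study entry. Section 4.2 adds observation and a visit one to two weeks after a research-only biopsy.

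Much of this stands. The case is narrow, the dates are illustrative, and a careful physician may well defer the biopsy. What can be shown is that the written criterion lacks the right reference date. It cannot be shown that patients go unprotected in practice.

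The gap remains all the same. The protocol set an explicit 6-week limit in addition to those general checks, and in this case the limit does not apply. Section 7.5 asks for the study to be run as written except in emergencies, so the literal wording matters. Observation and follow-up after the biopsy reduce the consequences but do not prevent the exposure. The reverse case (barred despite a long washout) carries no safety weight and is not counted as a harm.

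**Conclusion.** The concern holds. For non-accessible sites, 3.2.7 guarantees the intended 6 weeks only when no bevacizumab is given after enrollment. With a later dose, the interval it permits has no lower limit, and under the assumed dates it is 3 days against 42.

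The conclusion rests on the literal text of 3.2.7 and on the absence of a dose-to-biopsy interval for these sites elsewhere in the documents. The number of patients affected cannot be calculated, and only the research-only biopsy subset is exposed. The estimated proportion with a reportable variant, the 2-year PFS estimates, the precision table and the analysis methods are unaffected. Because the fault lies in a stated safety rule and the correction is a phrase, the sponsor should make it.

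**What to change.** In 3.2.7, change the reference date of the main sentence so that the exclusion applies to bevacizumab received *less than 6 weeks before the research biopsy*. Keep the 6-week and two-week lengths.

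Optionally, make the NOTE explicit in the same edit: *at least two weeks from the last dose to the biopsy*, stated as an exception to the 6-week rule for accessible sites. The NOTE already follows the right interval, so this is only for clarity.

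The cost is a wording amendment to one criterion, plus confirmation of the last-dose date at the pre-procedure check that 4.1.4 already requires. Sample size, endpoints and analysis do not change. Patients in the reverse case would become eligible for the biopsy without the single-subject exception process in 7.5.2.
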